## **Reports to the DSMB**

The NHLBI Lung DSMB as the independent data safety monitoring committee will review and approve the protocol before the enrollment. SAEs that meet the definition of an Unanticipated Problem will be submitted to the DSMB within 7 days of the investigator being notified of the event. DSMB will have access to safety data upon request any time. The monitoring plan will be developed and approved by the DSMB before enrollment. Additionally, the DSMB will be available for ad hoc reviews for AE/SAE, or safety concerns. The study will not stop enrollment awaiting these DSMB reviews, though the DSMB may recommend temporary or permanent stopping of enrollment based on their safety reviews.

### **8.4.7 Events of Special Interest**

N/A

### **8.4.8 Reporting of Pregnancy**

Pregnancy is not an AE. However, any pregnancy that occurs during study participation should be reported to the Sponsor on the appropriate CRF. Pregnancy should be followed to outcome.

## **8.5 UNANTICIPATED PROBLEMS**

### **8.5.1 Definition of Unanticipated Problems (UP)**

Any incident, experience, or outcome that meets **all** of the following criteria:

- Unexpected in terms of nature, severity, or frequency given (a) the research procedures that are described in the protocol-related documents, such as the Institutional Review Board (IRB)-approved research protocol and informed consent document; and (b) the characteristics of the participant population being studied; and
- Related or possibly related to participation in the research (“possibly related” means there is a reasonable possibility that the incident, experience, or outcome may have been caused by the procedures involved in the research); and
- Suggests that the research places participants or others (which many include research staff, family members or other individuals not directly participating in the research) at a greater risk of harm (including physical, psychological, economic, or social harm) than was previously known or expected.

### **8.5.2 Unanticipated Problem Reporting**

The investigator will report unanticipated problems (UPs) to the NIH Institutional Review Board (IRB) as per Policy 801.

### **8.5.3 NIH Intramural IRB Reporting of IND Safety Reports**

Only IND Safety Reports that meet the definition of an unanticipated problem will need to be reported to the NIH Intramural IRB.

## **9 STATISTICAL CONSIDERATIONS**

### **9.1 SAMPLE SIZE DETERMINATION**

This study plans to enroll approximately 60 eligible subjects, randomized in a 1:1 ratio to fostamatinib or placebo.

The primary outcome of the study is cumulative incidence of SAEs through day 29. Because of data on safety of the fostamatinib in combination with standard of care is unavailable, the sample size is determined by the feasibility to assess the activity and safety of the study treatment in a diverse group of hospitalized adults. As background standards of supportive care may evolve/improve over time as more is learned about successful management of COVID-19, comparisons of safety will be based on data from concurrently randomized subjects between fostamatinib and placebo arm. Randomization is essential to evaluate the safety and early efficacy of fostamatinib, which may lead to generalizable evidence of future confirmative studies.

### **9.2 POPULATIONS FOR ANALYSES**

#### **9.2.1 Evaluable for toxicity**

All randomized patients will be evaluated for toxicity from the time of their first treatment with study drug.

#### **9.2.2 Evaluable for primary analysis**

**All randomized patients who have received any study drug or placebo will be included in the primary outcome analysis**

### **9.3 STATISTICAL ANALYSES**

#### **9.3.1 General Approach**

Descriptive statistics will be used to summarize baseline characteristics and severity of illness. For continuous measures, the mean (standard deviation) or median (interquartile range) will be presented. For categorical variables, the frequency and the percentage in each category will be presented. All randomized patients receiving any study drug or placebo on study will be included in the safety analysis.

#### **9.3.2 Analysis of the Primary Endpoints**

Primary endpoint analysis will include descriptive statistics on the incidence of serious adverse events by the study arm. The difference in the percentages of SAEs between the treatment arms will be assessed by Fisher's exact test.

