**Description of Sites/Facilities Enrolling Participants:**

This will be a multicenter study. Enrollment will take place at the NIH Clinical Center and Inova health system hospitals with the potential of expanding to a 3rd site. We will enroll a total of approximately 60 evaluable patients . The study will be conducted exclusively in the United States.

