## **6.3 MEASURES TO MINIMIZE BIAS: RANDOMIZATION AND BLINDING**

### **6.3.1 Randomization**

The study will randomize subjects 1:1 to placebo or fostamatinib. Once a subject has completed the screening and baseline period and evaluation for inclusion/exclusion criteria, the randomization process will begin. The site investigator or designee will obtain the randomized assignment for that subject from the data coordinating center. Randomization will be stratified by site and severity of illness at enrollment. Severity of illness will be stratified into ordinal scale 5 and 6 (supplemental oxygen via nasal canula or non-invasive ventilation), mechanical ventilation, and ECMO.

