#### **9.3.3 Analysis of the Secondary Endpoint(s)**

To determine a subject's clinical status using the ordinal scale: On Day 1, report their clinical status at enrollment (start of study drug). On Day 2, report the period from enrollment to midnight on Day 1. On Day 3 through Day 11, or until discharged, and on Days 15, 22 and 29, provide the worst clinical assessment for the previous day (i.e., midnight to midnight; 00:00 –

23:59 (24-hr clock)). For example, on study Day 3 when completing the form, the worse clinical outcome measure of Day 2 is captured with the worst being death followed by ECMO, mechanical ventilation, etc. The Day 2 measurement is assessed as occurring anytime in that 24-hour period (00:00 to 23:59).

Secondary endpoints will be evaluated as follows:

1) The time to recovery by Day 29, it will be estimated by median and 95% confidence interval by study arm. The cumulative recovery rate will be estimated by the Kaplan-Meier method. The comparison between two treatment arms will be assessed by the log-rank test. The recovery ratio and hazard ratios will be based on the Cox model. The analysis will be stratified by disease severity at enrollment.

The time to recovery will be evaluate and censored up until Day 29. It is defined as the elapsed time in days from the day 1 to the earliest day at which a subject reaches recovery (having 1-3 of the 8-point ordinal scale). Any subjects that are lost to follow-up prior to an observed recovery will be censored at the day of their last observed assessment. Subjects who complete follow-up but do not experience recovery will be censored at Day 29. All deaths within Day 29 (and prior to recovery) will be considered censored at Day 29. Analysis will be based on intention to treat including all randomized patients. Patients who have received at least four doses of study drug will be considered in a sensitivity analysis for this secondary outcome.

2) Duration of events (e.g., mechanical ventilation or days in the ICU) will be summarized with median and interquartile rage by the study arms and compared between the treatment arms by Wilcoxon's rank sum test or log-rank test.

3) Binary events (e.g., need for intubation) will be summarized as percentages and 95% confidence intervals by the study arms and compared between the treatment arms by Fisher's exact test.

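### The primary SAE comparison names no confidence interval for the between-arm difference, and its pooled Fisher's exact test ignores the severity factor used to stratify randomisation

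*Combined protocol and SAP*

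**What the plan says.** Section 9.1 plans about 60 patients randomised 1:1. It states that "the sample size is determined by the feasibility", and that "comparisons of safety will be based on data from concurrently randomized subjects between fostamatinib and placebo arm". It gives no alpha, power or expected SAE rate.

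Section 9.3.2 is the whole of the primary analysis: descriptive SAE incidence by arm, then "The difference in the percentages of SAEs between the treatment arms will be assessed by" Fisher's exact test. Section 9.3.4 adds binomial intervals for the SAE proportions and a descriptive assessment of the difference between arms, with no interval method for that difference. Section 9.3.3, item 3, treats other binary events the same way: they are "summarized as percentages and 95% confidence intervals by the study arms" and then compared by Fisher's exact test.

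Section 6.3.1 says: "Randomization will be stratified by site and severity of illness at enrollment". It continues: "Severity of illness will be stratified into ordinal scale 5 and 6 (supplemental oxygen via nasal canula or non-invasive ventilation), mechanical ventilation, and ECMO". In section 9.3.3 the time-to-recovery analysis follows this design: "The analysis will be stratified by disease severity at enrollment". The primary comparison has no matching statement. Section 9.3.7 lists baseline severity as a subgroup, which does not adjust the overall comparison.

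**The concern.** The trial is sized by feasibility, and its stated purpose is a concurrent between-arm safety comparison. What such a trial can deliver is an estimate of the SAE difference and a statement of which excesses the data can exclude. A p-value from a conservative test on 30 patients per arm does not show that. For a harm endpoint, conservatism works in the unhelpful direction, because it makes a finding of no demonstrated difference more likely.

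Severity is already collected and used at randomisation. If it predicts SAEs, leaving it out of the primary comparison wastes precision. The plan adjusts a secondary endpoint for severity but not the primary one, and gives no reason.

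**Working it through.** **Inputs.** From the documents: about 60 patients, 1:1, so 30 per arm (9.1); a pooled Fisher test (9.3.2); severity strata of scale 5-6, mechanical ventilation and ECMO (6.3.1). Assumed, because the documents are silent: two-sided 5%, all SAE rates, the share of ventilated patients, the prognostic strength of severity, and no loss to follow-up. The plan states no power or precision figure that could be reproduced.

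**1. Size of Fisher's test.** Sum the product of the two binomial probabilities over all 31 x 31 tables with Fisher p at or below 0.05. At a common SAE rate of 10%, 20% and 30%, the true size is 0.9%, 2.2% and 2.6%.

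**2. What the p-value hides.** The Miettinen-Nurminen limits are the values of delta at which |d - delta| / sqrt{ N/(N-1) x [p1(1-p1)/n1 + p2(1-p2)/n2] } equals 1.96. Here d is the observed difference, and p1 and p2 are the maximum-likelihood rates constrained to differ by delta.

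| Fostamatinib vs placebo | Difference | Fisher p | 95% interval (points) |
|---|---|---|---|
| 10/30 vs 6/30 | +13.3 | 0.38 | -9.4 to +35.1 |
| 14/30 vs 6/30 | +26.7 | 0.054 | +2.7 to +48.1 |
| 15/30 vs 6/30 | +30.0 | 0.029 | not computed |

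In the second row, at delta = 0, the pooled rate is 20/60 = 0.333 and the variance is (60/59) x 0.333 x 0.667 x (2/30) = 0.01507. So z = 0.2667/0.1227 = 2.17 and p = 0.030. The interval excludes zero while Fisher does not reject. With 6/30 on placebo, Fisher needs 15/30 on fostamatinib.

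**3. What stratifying adds.** All two-stratum tables (scale 5-6 versus scale 7) were enumerated exactly, with fixed stratum sizes per arm, at a common odds ratio of 4. CMH is without continuity correction.

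| SAE risk on placebo, scale 5-6 / 7 | Ventilated | Fisher | Pooled Pearson | CMH |
|---|---|---|---|---|
| 15% / 60% (strong) | 10-40% | 42-49% | 54-59% | 64% |
| 15% / 40% (moderate) | 30% | 53% | 63% | 67% |
| 20% / 30% (weak) | 30% | 60.7% | 70.4% | 70.9% |
| 25% / 25% (none) | 30% | 63.6% | 73.0% | 73.1% |
| 30% / 15% (reversed) | 30% | 60.4% | 70.4% | 71.1% |

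Fisher to Pearson is the cost of Fisher's conservatism, about 9 to 12 points. Pearson to CMH is the gain from severity: about 5 to 9 points if strong, 4 if moderate, under 1 otherwise. The size of uncorrected CMH was 4.9 to 5.1% in all eight scenarios, including one with only 3 ventilated patients per arm. A continuity-corrected CMH loses most of the gain: size about 2%, power 51% (strong) and 63% (none). At an odds ratio of 3, uncorrected CMH still has only 43 to 52% power.

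**4. Interval performance.** The eight scenarios at odds ratios 1, 3, 4 and 6 give 32 settings. Coverage of a nominal 95% interval for the stratified risk difference was 92.8-93.8% (Wald), 94.8-97.6% (stratified Newcombe) and 94.6-95.4% (stratified Miettinen-Nurminen). Under no effect, the Miettinen-Nurminen half-width is about 20 to 22 points. With 30% ventilated it is 20.8 stratified against 22.6 pooled if severity is strongly prognostic, and 21.8 for both if it is not.

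**5. Agreement of test and interval.** With Mantel-Haenszel weight w = n1 n2/N in each stratum, the weighted Miettinen-Nurminen variance at zero difference is w^2 x N/(N-1) x p(1-p) x (1/n1 + 1/n2) = n1 n2 p(1-p)/(N-1). This is the CMH variance. The two statistics coincide at zero, so the interval and the uncorrected CMH p-value lead to the same decision.

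**The case against.** The strongest reply is that little is lost. Fisher's test is valid and is the plan's consistent choice for binary outcomes; omitting severity neither biases the comparison nor inflates type I error. Arm counts will be reported, so a reader can compute a pooled interval. For 10/30 versus 6/30, Newcombe's method built from the two single-arm Wilson limits gives -9.0 to +34.1, close to Miettinen-Nurminen. This stands, but it does not make a named, pre-specified interval unnecessary: printing two single-arm intervals side by side is not that calculation, and pooled counts do not yield the severity-adjusted one.

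The gain from stratifying is conditional. Section 8.4.4 treats conditions present before the first dose as baseline, so a weak or reversed severity gradient is plausible, and then almost nothing is gained. That also stands. In the scenarios examined, stratifying cost no power.

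The proposed analysis does not fully mirror the randomisation, since it drops site and merges ECMO with ventilation. Its fallback removes adjustment when imbalance is worst. With 3 ventilated patients in one arm and none in the other, at 15% and 60% risk and no treatment effect, the pooled difference is biased by (27 x 0.15 + 3 x 0.60)/30 - 0.15 = 4.5 points. This should be rare, the bias is small beside a half-width of 20 to 22 points, and every patient stays in the safety comparison.

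The DSMB boundary in section 9.3.6 and the listings in 9.3.4 protect patients during the trial and document events. They do not supply the final estimate.

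**Conclusion.** The point holds in both parts. No section names an interval for the between-arm SAE difference, and severity enters the time-to-recovery analysis but not the primary comparison.

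The missing interval is the essential part and does not depend on any prognostic assumption: at 30 per arm the uncertainty is about 20 to 22 points either side under no effect, and the planned test does not show it. Stratification is the lesser part. It ranges from nearly nothing to about 9 points of power at an odds ratio of 4, depending on how strongly severity predicts SAEs.

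This does not make the planned test invalid; it is a change that should be made before the analysis. All sizes rest on an assumed two-sided 5%, 30 per arm, and SAE rates and severity mixes that the documents do not give. No test at this sample size reliably detects a moderate excess.

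**What to change.** In section 9.3.2:

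1. Make the headline result the severity-stratified risk difference in the percentage of patients with at least one SAE through Day 29, with a 95% interval by the stratified Miettinen-Nurminen method with Mantel-Haenszel weights.
2. Test it with a Cochran-Mantel-Haenszel test without continuity correction on the same strata.
3. Define the strata as scale 5-6 versus scale 7, merging mechanical ventilation and ECMO. If scale 7 has no patients in one arm, use the unstratified versions. Leave site out and say why: two site groups by three severity levels give at least 6 cells, and 60/6 = 10 patients per cell is about 5 per arm, with a third site possible.
4. State the alpha and sidedness.
5. Keep pooled Fisher as a sensitivity analysis, and base the conclusion on the interval.

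The cost is SAP wording only, since severity is already recorded for randomisation. The downsides are that CMH is asymptotic, although its exact size was close to 5% in every scenario examined, and that the analysis will not reproduce every randomisation stratum. The text should also say how patients who withdraw before Day 29 are counted, because a patient-level percentage needs that rule.

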#### **9.3.3 Analysis of the Secondary Endpoint(s)**

To determine a subject's clinical status using the ordinal scale: On Day 1, report their clinical status at enrollment (start of study drug). On Day 2, report the period from enrollment to midnight on Day 1. On Day 3 through Day 11, or until discharged, and on Days 15, 22 and 29, provide the worst clinical assessment for the previous day (i.e., midnight to midnight; 00:00 –

23:59 (24-hr clock)). For example, on study Day 3 when completing the form, the worse clinical outcome measure of Day 2 is captured with the worst being death followed by ECMO, mechanical ventilation, etc. The Day 2 measurement is assessed as occurring anytime in that 24-hour period (00:00 to 23:59).

Secondary endpoints will be evaluated as follows:

1) The time to recovery by Day 29, it will be estimated by median and 95% confidence interval by study arm. The cumulative recovery rate will be estimated by the Kaplan-Meier method. The comparison between two treatment arms will be assessed by the log-rank test. The recovery ratio and hazard ratios will be based on the Cox model. The analysis will be stratified by disease severity at enrollment.

The time to recovery will be evaluate and censored up until Day 29. It is defined as the elapsed time in days from the day 1 to the earliest day at which a subject reaches recovery (having 1-3 of the 8-point ordinal scale). Any subjects that are lost to follow-up prior to an observed recovery will be censored at the day of their last observed assessment. Subjects who complete follow-up but do not experience recovery will be censored at Day 29. All deaths within Day 29 (and prior to recovery) will be considered censored at Day 29. Analysis will be based on intention to treat including all randomized patients. Patients who have received at least four doses of study drug will be considered in a sensitivity analysis for this secondary outcome.

2) Duration of events (e.g., mechanical ventilation or days in the ICU) will be summarized with median and interquartile rage by the study arms and compared between the treatment arms by Wilcoxon's rank sum test or log-rank test.

3) Binary events (e.g., need for intubation) will be summarized as percentages and 95% confidence intervals by the study arms and compared between the treatment arms by Fisher's exact test.

4) Mortality rate and the time to event endpoints will be estimated by Kaplan-Meier method and 95% confidence intervals by study arm and compared between the treatment arms by log-rank test.

5) Longitudinal measurements of each biomarker variables will be plotted over time. The mean and percent change from baseline for each variable will be estimated and compared to study arm using appropriate parametric or nonparametric tests and regression modeling.

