### **9.3.7 Sub-Group Analyses**

The following subgroups analysis will be performed.

- Symptoms duration >10 and ≤10 days
- Baseline disease severity
- Race (White, Black, Asian)
- Age (18 to <40, 40 to <66, ≥65)
- Sex (male and female)
- Concomitant therapies (e.g. treatment with and without remdesivir, steroids (dexamethasone, prednisone, hydrocortisone, methylprednisolone), convalescent plasma, tocilizumab or other immunomodulators intended for the treatment of COVID-19)
- Therapy with anti-coagulation by dose

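### The time-to-recovery Cox model is stratified by severity but leaves out age: the analysis is valid, but it may give up power and leaves the hazard ratio exposed to chance age imbalance

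*Combined protocol and SAP*

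**What the plan says.** Section 9.3.3, item 1, sets the analysis of time to recovery through Day 29. The arms are compared as follows: "The comparison between two treatment arms will be assessed by the log-rank test". The effect measure and the only adjustment are given in the next two sentences: "The recovery ratio and hazard ratios will be based on the Cox model. The analysis will be stratified by disease severity at enrollment". Neither age nor any other covariate is named.

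Section 6.3.1 stratifies randomization by site and by severity (ordinal 5 and 6 together, mechanical ventilation, ECMO). Age is not a stratum.

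Age has to be known to apply the entry criterion in section 5.1 (18 years or older, no upper limit). It is used in section 9.3.7 as a subgroup factor: "Age (18 to <40, 40 to <66, ≥65". As written, a 65-year-old falls in two of these bands.

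On size, section 9.1 states: "This study plans to enroll approximately 60 eligible subjects, randomized in a 1:1 ratio to fostamatinib or placebo". It adds that "the sample size is determined by the feasibility to assess the activity and safety of the study treatment". It gives no target hazard ratio, event count or power for recovery.

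**The concern.** With randomization stratified by site and severity only, age balance between two arms of about 30 is left to chance. If older patients recover more slowly than younger ones of the same severity, two things follow. An age gap between the arms moves the estimated hazard ratio, and nothing in the model corrects it. In addition, a Cox model without age estimates a smaller effect than one that conditions on age, so its test has less power.

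Banding age for subgroups repairs neither. At stake is part of the limited information this trial can give on early efficacy. There is also the awkwardness of an age adjustment added after the baseline table has been seen, which would be open to the charge of selection.

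**Working it through.** **The plan's own figure.** There is no power calculation to reproduce. Sixty patients at 1:1 gives 60/2 = 30 per arm, chosen for feasibility.

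**Chance age imbalance.** The difference in mean age between arms, in SD units, has standard deviation sqrt(2/30) = 0.258.
- P(gap > 0.25 SD, either direction) = 2[1 − Φ(0.25/0.258)] = 33%.
- P(gap > 0.5 SD) = 2[1 − Φ(0.5/0.258)] = 5%.
- In years, if the age SD is 14 (assumed): 14 × 0.258 = 3.6, so a gap above 4 years occurs in about 27% of trials. If the recovery hazard falls 3% per year (assumed), a 4-year gap alone shifts the hazard ratio by exp(0.03 × 4) = 1.13.

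**Simulation of the planned and proposed models.** From the documents: 60 patients, 1:1, severity strata, follow-up of about 28 days from Day 1. Assumed: two severity strata with 25% in the worse one, daily recovery hazards 0.085 and 0.025, normally distributed age, no deaths or dropout, and an age hazard ratio per SD of 1.0, 0.8, 0.65 or 0.5. There were 3,000 trials per row and about 46 to 52 recoveries per trial. Both models were fitted to the same simulated trials. Power is for the two-sided 5% Wald test of the treatment term; the version without age stands in for the severity-stratified log-rank test.

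| True HR | Age HR per SD | HR without age | HR with age | Power without | Power with |
|---|---|---|---|---|---|
| 1.5 | 1.0 | 1.50 | 1.50 | 27% | 28% |
| 1.5 | 0.8 | 1.49 | 1.52 | 27% | 30% |
| 1.5 | 0.65 | 1.44 | 1.51 | 23% | 28% |
| 1.5 | 0.5 | 1.40 | 1.53 | 21% | 28% |
| 2.0 | 1.0 | 2.05 | 2.08 | 69% | 69% |
| 2.0 | 0.8 | 1.98 | 2.05 | 64% | 67% |
| 2.0 | 0.65 | 1.87 | 2.03 | 56% | 65% |
| 2.0 | 0.5 | 1.76 | 2.05 | 47% | 66% |

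At a true hazard ratio of 1.0 the estimates stay at 1.00 and the rejection rate is 5% to 6% under either model.

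The SD of the log hazard ratio is slightly larger with age (for example 0.305 without and 0.313 with age, in the 2.0 / 0.65 row). The power gain therefore comes from an estimate further from 1, not from a narrower interval.

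**Effect of an age gap in the same runs.** Each 1 SD of imbalance moves the log hazard ratio without age by about −0.20 to −0.24, −0.38 to −0.44 and −0.58 to −0.59 for age hazard ratios of 0.8, 0.65 and 0.5. With age in the model the shift is about 0.

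**Does the pull toward 1 depend on sample size?** At n = 6,000 the model without age gives 1.49, 1.44 and 1.39 for a true 1.5, and 1.97, 1.85 and 1.71 for a true 2.0. The pattern matches n = 60. The shortfalls are (1.5 − 1.44)/1.5 = 4% and (2.0 − 1.85)/2.0 = 7.5% for the moderate age effect, and 7.3% and 14.5% for the strong one.

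**Cross-check with other assumptions.** These were a true HR of 2.0, age SD 14, daily hazard 0.075 and a 20% ventilated stratum with log-hazard −1.0, in 800 trials per age effect. For a hazard falling 2%, 3% and 4% per year, power rises from 0.61 to 0.65, 0.57 to 0.65 and 0.49 to 0.63. The 3% case equals exp(−0.03 × 14) = 0.66 per SD and agrees with the 0.65 row.

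**The case against.** The strongest reply is that nothing planned is wrong. A reader might infer that omitting age makes the hazard ratio biased or the analysis invalid. It does not: the severity-stratified hazard ratio without age is a legitimate quantity that is simply not conditional on age, and the log-rank test keeps its error rate. A reader might also infer that 30 per arm is what pulls the hazard ratio toward 1. The runs at n = 6,000 rule that out; only the chance imbalance depends on sample size. Both replies stand.

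Second, imbalance is symmetric and the planned interval already allows for it. With about 50 recoveries (assumed), SE(log HR) is about 2/sqrt(50) = 0.28. The shift of 0.12 on the log scale is then about 0.4 SE, inside a 95% interval reaching a factor of exp(1.96 × 0.283) = 1.74 each way. That is correct on average over trials. It does not help interpret the one trial in which the baseline table (section 9.3.5) shows an age gap.

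Third, the documents give no evidence that age predicts recovery. Listing it as a subgroup factor is not evidence, since sex, race and concomitant therapy are listed too. This stands, and is why the size is shown as a range that includes no effect.

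Fourth, the endpoint is one of 13 secondary endpoints in a safety trial sized by feasibility, and power is low regardless. By Schoenfeld's formula, 80% power needs 191 recoveries at a hazard ratio of 1.5 and 66 at 2.0. This limits the importance of the point but does not remove it, because the change costs almost nothing.

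**Conclusion.** The point holds as a missed gain in efficiency and credibility, not as an error. The severity-stratified Cox model without age is valid. If age predicts recovery within severity strata, it gives up roughly 3, 9 or 19 percentage points of power at a true hazard ratio of 2.0 (67 − 64, 65 − 56, 66 − 47), for weak, moderate and strong age effects. At 1.5 the loss is about 3, 5 or 7 points (30 − 27, 28 − 23, 28 − 21). It also leaves the estimate open to a chance age gap, which exceeds 0.25 SD in about a third of trials of this size. If age has no effect, neither model has a material advantage.

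These figures rest on assumed age effects, recovery rates, severity mix and true hazard ratios, none of which the documents supply. They concern a secondary endpoint only and do not touch the primary safety comparison.

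**What to change.** In section 9.3.3, item 1, before unblinding:
- Prespecify the Cox model stratified by severity, with treatment and age (continuous, in years) as terms, as the source of the main hazard ratio.
- State that the test of its treatment term is the one used to interpret this secondary endpoint. The section now assigns the comparison to the log-rank test, so without this sentence there would be two tests and no order between them.
- Report the severity-stratified log-rank test and the hazard ratio without age as supportive results.

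The cost is one parameter in one model, and no new data are needed. The small downside is that the main hazard ratio becomes conditional on age and should be labelled so.
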